Date: 2nd July 2018

Study code: 57BV1

Study title: Acute and chronic (28 days) effects of *Avena sativa* extract on physiological and psychological responses to stress, and mood and cognitive function

Ethics code: 10084

Study protocol

DESIGN

The study will follow a randomised, double-blind, placebo-controlled, parallel groups design.

PROCEDURE

Testing will take place in a suite of testing facilities with participants visually isolated from each other. Participants will attend the laboratory on 3 separate occasions, an introductory visit between 1 and 14 days before the first day of treatment, and two testing days (Day 1 and Day 29).

The Introductory visit to the laboratory will comprise: briefing on requirements of the study, obtaining of informed consent, health screening, completion of the Caffeine Consumption Questionnaire (CCQ) and State-Trait Anxiety Inventory (STAI) trait subscale, training on the cognitive and mood measures and collection of demographic data. Participants will also complete the baseline Cognim^{app} assessment of mood (GAD-7, Bond-Lader, VAS).

For the two ensuing laboratory-based testing sessions (Day 1, Day 29) participants will attend the laboratory before 8.00 am having consumed a standardised breakfast of cereal and/ or toast at home no later than an hour before arrival. They must have refrained from alcohol for 24 hours and caffeine for 18 hours. The methodology during these visits will be identical. On arrival on each day participants will complete the GHQ-12 (mental health) and POMS (Mood/depression/arousal). Each subsequent assessment will comprise a short set of cognitive tasks (Corsi Blocks, Stroop, RVIP, Numeric Working Memory – 12 minutes) and completion of the Observed Multitasking Stressor (OMS) test session. This 15 minute OMS takes place in front of a panel of three observers, and comprises provision of a saliva sample, completion of the Perceived Stress Scale (PSS) (before the stressor only) followed by STAI-state, Bond-Lader Mood Scales and visual analogue scales (VAS) which are completed before and after the stressor. The stressor comprises the performance of three separate verbal serial subtraction tasks (Serial 3s, Serial 7s, Serial 17s – 4 minutes per task) whilst concomitantly performing a computerised tracking task. Finally a further saliva sample is taken. Heart rate and galvanic skin response (GSR) are recorded throughout.

After the first cognitive/OMS assessment participants will take their treatment for the day and will undergo identical Cognitive/OMS assessments commencing 120 and 240 minutes post-dose. Following completion of the final assessment at 240 min post-dose participants will complete the GHQ-12 and POMS (to assess any general effects on anxiety, depression, and mood).

Additionally, an interim mood assessment (GAD-7, Bond-Lader, VAS) in the participant's own home, delivered using Cognim^{app} software by mobile phone or the internet, will be included at weekly intervals (Day 8, 15, 22) between laboratory visits with a final assessment during Day 29.

Figures 1 depicts the running order of the OMS and Figures 2 and 3 depict the laboratory-based testing session timeline and chronic study overview respectively.

[figure not shown]

Figure 1. Cognitive, mood and Observed Multitasking Stress assessment. Participants complete a short cognitive assessment (executive function, attention and working memory) in the general laboratory and then move to the interview room. They provide a saliva sample (cortisol/α-amylase) and complete the Perceived Stress Scale. They then complete the STAI, Bond-Lader, and VAS before and after the completion of three 4-minute verbal Serial Subtraction tasks (Serial 3s, 7s, 17s, completed in counterbalanced order) and a concomitant computerised tracking task. Heart rate (HR) and galvanic skin response (GSR) are measured throughout performance of the tasks. A further saliva sample is taken at the end of testing.

[figure not shown]

Figure 2. Schedule of each testing session (Day 1, Day 29). Participants complete the POMS and GHQ-12, followed by the cognitive tasks (in the lab). They then move to the interview room and complete the Observed Multitasking Stressor assessment. After this they take their day's treatment, and then complete further identical cognitive/OMS assessments commencing 120- and 240 min post-dose. Between these two post-dose assessments, participants will be provided with a standardised lunch. Before departing they complete the POMS and GHQ-12.

[figure not shown]

Figure 3. Study timelines. Participants attend an introductory/screening session -1 to -14 days before the first (acute dose) study day (Day 1). They then undergo an identical assessment on Day 29 of the treatment schedule. Brief mood assessments are completed in the participants home using Cognimapp pre-treatment and after 8, 15, 22 days treatment – the final assessment takes place in the laboratory on Day 29.

Study analysis plan

The cognitive, mood, and psychological/physiological stress response data may be subjected to several baseline adjusted ANOVA¹ analyses in order to assess:

¹ Alternative analyses include ANCOVA in the event of any influence of demographic/mood parameters on the outcomes (e.g. age, anxiety) and/or Linear mixed models in the case of missing data.

- The acute effects of treatment (Day 1 data from 120/240 min post-dose baseline adjusted to Day 1 baseline – ANOVA factors: assessment x treatment)
- The effects of chronic supplementation on the acute effects of the treatment (Day 1 and Day 29 data from 120/240 min post-dose baseline adjusted to the respective day's pre-dose data ANOVA factors: day x assessment x treatment)
- The pure chronic effects of treatment (Day 29 pre-dose data baseline adjusted to Day 1 pre-dose AND Cognim^{app} mood data from Day 8, 15, 22 and 29 baseline adjusted to the pre-dose assessment ANOVA factors: day x treatment)
- The chronic with acute superimposed effects of treatment (Day 29 pre-dose, 120, 240 min data baseline adjusted to Day 1 pre-dose - ANOVA factors: assessment x treatment)

The above analyses will be applied, as appropriate, to the following data:

- General mood, including depression and anxiety (POMS, GHQ-12 – measured pre dose and at the end of testing on Day 1 and Day 29).
- General mood/psychological state (GAD-7, Bond-Lader, VAS) measured pre-treatment and on Days 8, 15, 22, 29 using Cognim^{app}.
- Cognitive function – executive [Stroop], attention [RVIP], working memory [Corsi blocks, NWM] –pre-dose [chronic only] and at 120 and 240 minutes post-dose.
- Overall mood and psychological state measured pre-dose and at 120 and 240 mins post-dose (PSS, STAI, Bond-Lader VAS – measured pre-OMS)
- Overall cognitive performance during the OMS pre-dose and at 120 and 240 mins post-dose (accuracy and speed of Serial 3s, 7s, 17s, computerised tracking task)
- Overall stress hormone levels (salivary cortisol, α -amylase) measured before the OMS pre-dose [chronic only] and at 120 and 240 min post-dose.
- Modulation of the psychological response to acute stress (change in: PSS, STAI, Bond-Lader, VAS during the OMS) as a consequence of the OMS pre-dose and at 120 and 240 mins post-dose.
- Modulation of the physiological response to acute stress (change in heart rate, galvanic skin response, salivary cortisol, α -amylase during OMS) as a consequence of the OMS pre-dose and at 120 and 240 mins post-dose.

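### *Baseline adjusted* ANOVA is not defined; if it means subtracting each outcome's baseline, fitting that baseline as a covariate would give more precise treatment effects from the same data

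*Combined protocol and SAP*

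**What the plan says.** The study analysis plan says the data may undergo several baseline-adjusted ANOVAs and lists four. None defines the adjustment, and each names only factors drawn from day, assessment and treatment.

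- Acute: "Day 1 data from 120/240 min post-dose baseline adjusted to Day 1 baseline".
- Effect of supplementation on the acute response: each day's post-dose values are referred to that day's own pre-dose value ("pre-dose data ANOVA factors: day x assessment x treatment").
- Pure chronic: "Day 29 pre-dose data baseline adjusted to Day 1 pre-dose" for laboratory outcomes, and "mood data from Day 8, 15, 22 and 29 baseline adjusted to the pre-dose assessment" for the app scores, whose baseline is taken at the introductory visit.
- Chronic with acute superimposed: "Day 29 pre-dose, 120, 240 min data baseline adjusted to Day 1 pre-dose".

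Footnote 1 adds: "Alternative analyses include ANCOVA in the event of any influence of demographic/mood parameters on the outcomes", giving age and anxiety as examples. It offers linear mixed models for missing data. It does not mention the outcome's own baseline.

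The number of follow-ups differs by outcome. Most laboratory outcomes have two post-dose values per testing day. POMS and GHQ-12 are "measured pre dose and at the end of testing on Day 1 and Day 29", so they have one; the Procedure section agrees ("Following completion of the final assessment at 240 min post-dose participants will complete the GHQ-12 and POMS").

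**The concern.** If the outcome's own baseline were already a covariate, the main method would itself be an ANCOVA, and listing ANCOVA as an alternative would make little sense. This points to subtraction, which fixes the slope of follow-up on baseline at 1. Fitting the baseline as a covariate estimates that slope instead. When the true slope is not 1, subtraction leaves baseline noise in the treatment comparison that could have been removed.

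Two things are at stake. Confidence intervals for the acute, chronic and chronic-with-acute effects may be wider than they need be. And because the term is undefined, two analysts could fit different models to the same outcome, with nothing in the plan to say which was intended.

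**Working it through.** **Inputs from the documents.** Randomised, parallel groups; the Day 1 assessment precedes the first dose, and the app baseline precedes treatment. The acute analysis has one baseline and two follow-ups (120 and 240 min) for most outcomes. There is no figure of the plan's own to reproduce.

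**Assumptions.** The documents give no sample size, number of arms, SD or correlation. I take baseline and follow-up variances of 1 and one common correlation r, with r = 0.3, 0.5, 0.7, 0.9. Where a sample size is needed I take two arms of n = 30.

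**General result.** Let B be the baseline, Y the follow-up (or the mean of several), and b = Cov(Y,B)/Var(B).

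- Subtraction: Var(Y − B) = Var(Y) + Var(B)(1 − 2b)
- Covariate, large samples: Var(Y) − b²Var(B)
- Difference: Var(B)(1 − b)², which is never negative and is zero only at b = 1.

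**Size under the assumptions.** For the mean of K follow-ups, Var(Y) = (1 + (K − 1)r)/K and b = r. The subtraction/covariate variance ratio is then (K + 1)/(1 + Kr): 2/(1 + r) for K = 1 and 3/(1 + 2r) for K = 2.

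| r | One follow-up | Mean of 120/240 min |
|---|---|---|
| 0.3 | 2/1.3 = 1.54 | 3/1.6 = 1.88 |
| 0.5 | 2/1.5 = 1.33 | 3/2.0 = 1.50 |
| 0.7 | 2/1.7 = 1.18 | 3/2.4 = 1.25 |
| 0.9 | 2/1.9 = 1.05 | 3/2.8 = 1.07 |

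Taking square roots, intervals are 24% to 3% wider for one follow-up and 37% to 4% wider for the mean of two.

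**Cost of estimating the slope.** With a normal baseline, the covariate variance is multiplied by 1 + 1/(2n − 4) = 1 + 1/56 = 1.018 at n = 30. The ratios become 1.51, 1.31, 1.16, 1.03 (one follow-up) and 1.84, 1.47, 1.23, 1.05 (mean of two). A simulation of 20,000 trials at n = 30 gave 1.54, 1.30, 1.15, 1.04 and 1.83, 1.47, 1.24, 1.05, within about 2% of theory. All mean estimates were within 0.004 of the true zero.

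**Break-even at n = 30.** Setting 2/(1 + r) = 1.018 gives r = 0.965; setting 3/(1 + 2r) = 1.018 gives r = 0.974. These hold only with equal variances and equal correlations. In general break-even depends on b, which for one follow-up is r × (follow-up SD / baseline SD).

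**Sensitivity to the assumptions.**

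- One follow-up, r = 0.7, SD ratio 1.2: subtraction 1.44 + 1 − 1.68 = 0.76; covariate 1.44 × 0.51 = 0.7344; ratio 1.035, not 1.18.
- One follow-up, r = 0.8, SD ratio 1.25: b = 1, so the ratio is 1.00 and subtraction saves the small slope cost.
- Mean of two, correlation 0.5 with baseline and 0.8 between 120 and 240 min: Var(Y) = 0.9; subtraction 0.9 + 1 − 1 = 0.90; covariate 0.9 − 0.25 = 0.65; ratio 1.38, not 1.50.

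**Where there is no gain.** In a contrast between two follow-ups with the same baseline (240 minus 120 min, or day by treatment in the app data), the baseline cancels. Fitting a slope to such a contrast gave simulated covariate/subtraction ratios of 1.01 to 1.03 at an assumed 20 to 66 per arm.

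**The three-factor analysis.** Its Day 29 baseline follows weeks of treatment. Suppose treatment has moved the Day 29 pre-dose mean by d and that day's dose adds nothing. The true within-day effect is zero, but with the Day 29 pre-dose value as a covariate the estimate is d − bd = d(1 − b). Within-day change gives d − d = 0.

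**The case against.** The strongest objection is that the loss is conditional. Only the absence of a definition is certain; subtraction is inferred from labels. Some wording points the other way: when the plan describes the response to the stressor it speaks of a change, and here it uses a different term. The plan is also permissive about which analyses will be run, and footnote 1 keeps ANCOVA and mixed models available. This stands, so the precision loss must be stated as conditional. It does not remove the point, because the footnote never names the outcome's own baseline.

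The second objection is that the larger ratios rest on convenient assumptions. This also stands. Equal variances and one common correlation are not in the documents, and the sensitivity cases show the gain shrinking or vanishing. A follow-up SD below the baseline SD can equally enlarge it.

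Third, several terms the plan lists are untouched: treatment by assessment within a day, and day by treatment in the app data.

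A reader might infer more than this: that the plan definitely uses change scores, that its treatment effects would be biased, or that every listed analysis loses precision. The documents support none of these. The method is unstated, randomisation makes both methods unbiased where the baseline precedes treatment, and contrasts sharing a baseline are unaffected.

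**Conclusion.** The point holds in conditional form. The term is undefined, and subtraction is the more natural but unconfirmed reading. If it is what was meant, the default gives up precision for effects at a single follow-up (Day 29 pre-dose; Day 1 POMS and GHQ-12) and for effects averaged over follow-ups.

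The tabulated ratios are illustrations, not estimates for this trial. They do not apply if percentage change was intended. Against a gain that may be anywhere from nil to substantial, the cost of the covariate is small. This is an improvement the sponsor should make; it does not threaten validity.

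**What to change.** Define the adjustment in the study analysis plan.

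- **Acute Day 1, pure chronic, app-mood and chronic-with-acute analyses:** model the follow-up value by ANCOVA or a linear mixed model, with that outcome's own Day 1 pre-dose value as a covariate (introductory-visit value for app scores).
- **More than one follow-up:** include assessment or day and its interaction with treatment.
- **One follow-up (Day 29 pre-dose laboratory outcomes in the pure chronic analysis; Day 1 POMS and GHQ-12):** fit treatment plus baseline only.
- **Three-factor analysis of day, assessment and treatment:** keep the within-day change, and do not use the Day 29 pre-dose value as a covariate. Note that its Day 1 estimate will differ slightly from that of the acute analysis.
- **If a covariate was already intended:** say so and reword footnote 1, so that ANCOVA no longer appears only as an alternative for demographic and mood variables.

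The cost is a few sentences and one estimated slope per outcome, or one per occasion if baseline-by-occasion terms are fitted. One slope adds about 2% to the variance at an assumed 30 per arm. No new data are needed.

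### Does the analysis of chronic with acute superimposed effects need a prespecified contrast because its ANOVA terms miss the combined Day 29 effect?

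*Combined protocol and SAP*

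**What the plan says.** The Study analysis plan lists four baseline-adjusted ANOVAs. The fourth is headed "The chronic with acute superimposed effects of treatment" and is specified as "Day 29 pre-dose, 120, 240 min data baseline adjusted to Day 1 pre-dose - ANOVA factors: assessment x treatment".

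The timing comes from the Procedure section: "After the first cognitive/OMS assessment participants will take their treatment for the day", with further assessments starting 120 and 240 minutes after the dose. Day 29 pre-dose therefore reflects the preceding weeks of treatment and not that day's dose. The third bullet uses it that way, as the pure chronic outcome: "Day 29 pre-dose data baseline adjusted to Day 1 pre-dose".

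The second bullet takes "Day 1 and Day 29 data from 120/240 min post-dose baseline adjusted to the respective" day's pre-dose value, which isolates same-day effects on both days. The footnote allows ANCOVA, or "Linear mixed models in the case of missing data". None of the four bullets names a contrast, a simple effect, or the ANOVA term that answers its question.

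**The concern.** The title of the fourth analysis suggests one quantity: the chronic effect plus the acute effect on top of it, as seen after the Day 29 dose. One of the three assessment levels has no acute effect to add. The treatment main effect averages over that level, and the interaction removes the chronic part altogether, so neither standard term is the combined post-dose effect. The other three bullets do not list it as a term either: the first and second subtract the same day's pre-dose value, and the third stops at pre-dose.

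If the main effect were reported as the combined effect, it would be too small when chronic and acute effects share a sign or the chronic effect is nil, and too large when the acute effect opposes a larger chronic one. With no stated contrast, the analyst could also choose among a main effect, an interaction and per-time tests after seeing the data, for many outcomes.

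**Working it through.** The documents give no sample size, SD, alpha or effect size, so there is no planned figure to reproduce. The assessment times and factors come from the fourth bullet, and the order of dose and assessment from the Procedure section.

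**What each term estimates.** The treatment-minus-placebo differences on Day 29, adjusted to Day 1 pre-dose, are c at pre-dose, c + a120 at 120 min and c + a240 at 240 min.

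- Main effect, equal weights: [c + (c + a120) + (c + a240)]/3 = c + (a120 + a240)/3. With a120 = a240 = a this is c + 2a/3.
- Interaction: differences from pre-dose are a120 and a240; c cancels.
- Mean of the two post-dose times: c + (a120 + a240)/2 = c + a when the two are equal.

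**Size of the gap if the main effect is read as c + a.** The share is (c + 2a/3)/(c + a):

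| Case | Share |
|---|---|
| c = 0 | 67% |
| c = a/2 | 78% |
| c = a | 83% |
| c = 2a | 89% |
| a = 0 | 100% |
| a = -c/2 | 133% |

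These shares need no assumption about variance. They do need the main effect to be read in a way the plan does not state.

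**Would a post-dose average be better?** Assume unit SDs, change scores, a correlation of 0.6 between all times, two-sided 5%, and 80% power for the post-dose average (z = 2.80).

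- Variance of the two-time average minus baseline: (1 + 0.6)/2 + 1 - 1.2 = 0.600.
- Variance of the three-time average minus baseline: (1 + 1.2)/3 + 1 - 1.2 = 0.533.
- Precision factor in favour of the main effect: sqrt(0.600/0.533) = 1.061.
- At c = a: 2.80 x 0.833 x 1.061 = 2.47, so main-effect power is Phi(2.47 - 1.96) = 70%, against 80%.
- At a = 0: 2.80 x 1.061 = 2.97, so main-effect power is 84%, against 80%.
- Break-even: a/c = (1.061 - 1)/(1 - 2 x 1.061/3) = 0.21. Over other plausible correlations, and with ANCOVA, it runs from 0.03 to 0.35.

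The better choice therefore turns on a/c, which is unknown. Averaging 120 and 240 min also dilutes an effect present at only one of them. With c = 0 and a same-day effect A at one time, the main effect is A/3, the post-dose average A/2, and the per-time comparison A.

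**Do the second and third analyses leave a large power gap?** Take c = a, so each part is half of c + a. The Day 29 same-day contrast alone has variance 0.60: z = 2.80 x 0.5 x sqrt(0.60/0.60) = 1.40, power 29%. The second bullet's treatment main effect pools both days. If the Day 1 same-day effect also equals a, its variance is 0.30: z = 1.40 x sqrt(0.60/0.30) = 1.98, power 51%. With same-day correlation 0.8 and cross-day correlation 0.6, the variances for c + a, Day 29 alone and pooled are 0.70, 0.30 and 0.15. Power is then 57% for Day 29 alone (z = 1.40 x sqrt(0.70/0.30) = 2.14) and 86% pooled (z = 1.40 x sqrt(0.70/0.15) = 3.02), against 80% for c + a. The pooled advantage shrinks if the Day 1 effect is smaller than a.

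**The case for a change.** The strongest case for a change is that an edited bullet costs almost nothing, that superimposed does not naturally describe an average with a pre-dose time, and that naming the contrast in advance removes a choice otherwise made with the data in hand. The algebra supports it, and the absence of any stated contrast is a fact.

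What stands is a gap in detail. The bullet lists model factors and nominates no answer, and contrasts are absent from all four analyses, so the gap is not peculiar to this one. The heading speaks of effects in the plural and deliberately keeps pre-dose beside 120 and 240 min. That fits a Day 29 profile: the chronic level at pre-dose, then the acute change laid on it, described by treatment and interaction together. Under that reading pre-dose is the reference that makes the acute part visible, and the main effect is a valid session average.

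Two supporting arguments are weak. In a mixed model with pre-dose as reference level, the treatment coefficient is indeed c alone, but that coefficient is not the main-effect test; marginal means or sum-to-zero coding give the equally weighted effect. The argument that the second and third analyses are a poor substitute because each has much lower power also fails to hold generally, as the pooled figures show.

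**Conclusion.** No change to the plan is needed. The three-level main effect is c + 2a/3 under equal weights and equal acute effects at the two post-dose times, so it should not be described as the combined post-dose effect; the plan does not describe it so. Analysts would fill the gap from the same fitted model, reading treatment differences at 120 and 240 min against Day 1 pre-dose, with the interaction for the acute part. That needs no new data and alters no stated decision rule, since the plan names no primary analysis.

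Replacing the main effect by a post-dose average would be a trade-off. Under the assumed correlation of 0.6 it moves power from 70% to 80% when c = a and from 84% to 80% when a = 0, and it loses to per-time comparisons if the effect appears at one time only. The 67% to 133% shares are exact but conditional on a misreading; every power figure rests on assumed correlations, alpha and effect size.
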